#### **8.4. Structural Modification Assessments**

##### **8.4.i. Posterior-Anterior Hand Radiographs (Obtained at the baseline and 24 week follow up visits)**

Standardized bilateral posterior-anterior hand radiographs will be obtained on all participants using the same standardized operating procedure to minimize variability between studies. These images will be scored for Kellgren and Lawrence scores (primary structure outcome), joint space narrowing, and osteophyte scores, and Verbruggen-Veys in the DIP joints by our collaborator, [name], paired and as a batch once the study is completed.

**8.4.ii Selecting Participants for Specialized Imaging to Assess Proof of Concept and MRIs.** To select people who will get a single DIP high resolution MRI at week 2 and at 6 month follow-up, we will select 3 women and 2 men from each treatment group who are matched by age within 10 years. To assess the biologic effect of the traction orthosis, we plan to obtain x-rays before and after application of the orthoses during the one month follow up visit. We will select 5 men and 5 women to participate in this activity at this follow up visit to have the radiographs with and without the traction orthosis. We will make every attempt to include the 5 people who will have an MRI performed of one DIP to be included in this group.

##### **8.4.iii. High Resolution MRI Imaging (Obtained at the week 2 and 24 week follow up visits)**

On 5 participants in each treatment arm (for a total of 10 participants), we will obtain high resolution MRI imaging of the most symptomatic DIP joint.

The sequences that will be obtained will include the following:

- 3-Plane Localizer
- Coronal T1
- Coronal Proton Density
- Coronal T2 Fat Suppressed
- Axial T1
- Sagittal Merge 3D
- Coronal T1 Fat Suppressed with Gadolinium
- Axial T1 Fat Suppressed with Gadolinium

Our collaborator, [name], will score all these MRIs, paired and as a batch once the study is completed for collateral ligament thickening, enthesial bone marrow edema, and erosions.

### **8.5 Proof of Concept.**

At the 2 week follow up visit, 10 participants, 5 men and 5 women, receiving traction will be asked to have radiographs of the hand with and without the traction orthosis applied to assess whether applying this treatment results in an increase in joint space width.

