**Not Done (ND)** – When recording data on a study form, if the evaluation required for a field is not done, then the acronym ND should be used to fill out the field.

**Occupational Therapist (OT)** – This is our study staff who provides occupational therapy to our participants and fits the participants with either the hand-based traction orthosis or the resting orthosis.

**Office for Human Research Protection (OHRP)** – A federal government agency within the Department of Health and Human Services (DHHS) charged with the protection of human subjects participating in government-supported research. The OHRP issues assurances to institutions reviewing human subjects research and oversees compliance of regulatory guidelines by research institutions.

**Osteoarthritis (OA)** – a common form of joint disease that most often affects the hands, hips, knees and feet and is the subject of study in this clinical trial.

**Posterior-Anterior (PA)** – Describes the direction that a radiograph is acquired.

**Principal Investigator (PI)** – The individual with primary responsibility for achieving the technical success of the project, while also complying with the financial rules and requirements, administrative policies, and regulations associated with a grant or award. Although Principal Investigators may have administrative staff to assist them with the management of project funds, the ultimate responsibility for the management of the research project rests with the Principal Investigator.

**Proof of Concept (POC)** – Describes the radiographs that evaluate the change in joint space that occurs with application of the traction and the resting orthoses.

**Quality Control (QC)** – The internal operational techniques and activities undertaken within the quality assurance system to verify that the requirements for quality of trial related activities have been fulfilled (e.g., data and form checks, monitoring by study staff, routine reports, correction actions, etc.).

**Research Coordinator (RC)** – An individual that handles the administrative and day-to-day responsibilities of a clinical trial. This person may collect or review data before it is entered in the study database.

**Safety Monitoring Plan (SMP)** – A plan that outlines the oversight of a clinical trial.

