**1.1 Schedule of Activities (SoA)*****The schedule below is what is planned for our participants.***

Procedures	-4	Screening Visit - Day -30 to -1	Enrollment/Baseline Visit 1, Day 1 +/-7 days	Reminder Visit 1, Day 7 +/-3 days	Study Visit 2, Day 14 +/- 7 days	Reminder Visit 2, Day 21 +/- 3 days	Study Visit 3, Day 28 +/- 7 days	Reminder Visit 3, Day 35 +/- 3 days	Reminder Visit 4, Day 42 +/- 3 days	Reminder Visit 5, Day 49 +/- 3 days	Reminder Visit 6, Day 56 +/- 3 days	Reminder Visit 7, Day 63 +/- 3 days	Reminder Visit 8, Day 70 +/- 3 days	Reminder Visit 9, Day 77 +/- 3 days	Reminder Visit 10, Day 84 +/- 14 days	Reminder Visit 11, Day 98 +/- 3 days	Reminder Visit 12, Day 105 +/- 3 days	Reminder Visit 13, Day 112 +/- 3 days	Reminder Visit 14, Day 119 +/- 3 days	Reminder Visit 15, Day 126 +/- 3 days	Reminder Visit 16, Day 133 +/- 3 days	Reminder Visit 17, Day 140 +/- 3 days	Reminder Visit 18, Day 147 +/- 3 days	Reminder Visit 19, Day 154 +/- 3 days	Reminder Visit 29, Day 161 +/- 3 days	Final Study Visit, Day 168 +/- 14 days
Week	0																									
Screening Questionnaire	X																									
Eligibility Assessment	X																									
Baseline Demographics	X																									
Randomization	X																									
Create either the traction v resting hand orthosis	X																									
Repeated measures evaluation	X						X																			X
Hand photographs	X						X																			X
PA Radiographs	X																									X
MRI Screener	X																									X
Serum creatinine a	X																									X
Urine Pregnancy test b	X																									X
Proof of Concept Radiographs c						X																				
MRI of the most symptomatic DIP joint c					X																					X
Weekly Reminders (telephone, text, or email)		X	X	X	X	X	X	X	X	X	X	X	X	X	X	X	X	X	X	X	X	X	X	X		
Adverse Event and Review		X	X	X	X	X	X	X	X	X	X	X	X	X	X	X	X	X	X	X	X	X	X	X		
Final Visit Assessment Questions																										X

**Table 1. Schedule of Activities.**a Only for those being screened for MRIb Only for those of childbearing age who are womenc Only for a selected group of 10 participants

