### 3.0 Study Objectives

**Specific aim 1. Feasibility of a static hand based orthosis to apply finger traps.** The study OT will customize a static hand based orthosis that allows convenient application of finger traps for those receiving traction. We will record issues related to creating the traction orthoses, ease/difficulty of applying the intervention, comfort level while wearing the orthosis, hand pain, and compliance of wearing the orthosis. At the final study visit, we will also ask whether participants plan to use the orthosis after completion of the study.

**Specific aim 2. Proof of concept.** For 10 participants, 5 participants in each arm that are age and sex matched, at the two week follow up, we will obtain radiographs of the hand *with* and *without* orthoses applied to assess whether applying the traction orthosis results in an increase in joint space width.

**Specific aim 3. Symptomatic and functional outcomes.** At baseline, 1 month, 3 months, and 6 months follow up, we will assess outcomes including the visual analog scale (VAS) in the more symptomatic hand that includes the most symptomatic DIP joint (primary symptom outcome), the VAS pain scale of the most painful DIP, the AUSCAN function subscale, the Functional Index for Hand Osteoarthritis (FIHOA), the Disabilities of the Arm, Shoulder, and Hand (DASH), the Functional Dexterity Test, grip and pinch strength, and tenderness on joint palpation on all participants.

**Specific aim 4. Imaging outcomes.** On all participants, we will obtain bilateral hand radiographs at baseline and at 6 months to assess changes in Kellgren and Lawrence scores (primary structure outcome), joint space narrowing, and osteophyte scores, and Verbruggen-Veys in the DIP joints. On 5 participants in each treatment arm (age and sex matched), we will obtain high resolution MRI imaging at week 2 and at 6 months to evaluate collateral ligament thickening, enthesial bone marrow edema, and erosions of the most symptomatic DIP.

OBJECTIVES	ENDPOINTS	JUSTIFICATION FOR ENDPOINTS
Primary		

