#### **4.3 Subject Participation Duration**

##### **4.3.a Study Participation Duration:**

- **Week -1:** Screening Visit (phone or email) (10 - 20 minutes) – Assess preliminary eligibility criteria
- **Week 0:** Eligibility/Baseline Visit (6 hours) – assess eligibility criteria, obtain informed consent, all clinical outcome assessments, hand x-rays, prescreening assessment for MRI, hand therapist will provide non-pharmacologic therapies for hand OA, randomization allocation, creation of hand orthosis based on randomization allocation.
- **Week 2:** Study Visit (0.5 – 3 hours) – All participants: hand therapist assess orthosis fit; for selected 10 people: proof of concept X-rays, with and without orthoses in place AND MRI of one finger DIP
- **Week 4:** Study Visit (1.5 hours) – all clinical outcome assessments, hand therapist assess orthosis fit.
- **Week 4 – 6:** Study Visit (0.5 hours) – MD visit if requested.
- **Week 12:** Study Visit (1 hour) – all clinical outcome assessments.
- **Week 24:** Study Visit (3-4 hours) – all clinical outcome assessments, bilateral hand X-rays, follow up MRI (if it was done at week 2).

**4.3.b Study Duration:** The estimated time between when study opens for enrollment and final data collection occurs is 18 months. The estimated time between when study opens for enrollment and final data analysis is completed is 30 months.

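### The Aim 2 proof-of-concept films are given two incompatible groups and two visits, and Section 9 reads a narrowing score where the aim asks about joint space width

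*Combined protocol and SAP*

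**What the plan says.** **Group.** Section 3.0, Specific aim 2, reads "For 10 participants, 5 participants in each arm that are age and sex matched, at the two week follow up, we will obtain radiographs". Section 10.7.b agrees: the films are taken on the same ten people who have MRI, two men and three women in each arm. The glossary entry for Proof of Concept also covers both arms: "Describes the radiographs that evaluate the change in joint space that occurs with application of the traction and the resting orthoses". The Schedule of Activities (Section 1.1) attaches one footnote to both the films and the MRI, "Only for a selected group of 10 participants", and Section 4.3.a puts them in one line at week 2: "for selected 10 people: proof of concept X-rays, with and without orthoses in place AND MRI of one finger DIP".

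Section 8.5 differs: "10 participants, 5 men and 5 women, receiving traction will be asked to have radiographs of the hand with and without the traction orthosis". Section 8.4.ii likewise asks for five men and five women, filmed with and without the traction orthosis. It undertakes only to try to include five people who have MRI, although ten people have MRI.

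**Visit.** Sections 3.0, 4.3.a, 8.5 and 10.7.b place the films at week 2. Section 8.4.ii places them at the one-month visit.

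**Measure.** Aim 2 is "to assess whether applying the traction orthosis results in an increase in joint space width", and Section 8.5 asks the same. Section 9.0, Specific aim 2, instead plans a subjective paired reading for improvement in a joint space narrowing score, without formal statistics.

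**The concern.** Every version fixes the total at ten, so they are competing definitions of one group and cannot be added together. Staff selecting participants from Section 8.4.ii would choose different people, at a different visit, from staff working from Section 10.7.b.

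The choice sets how many traction hands support the proof of concept, whether any resting-orthosis hands stand beside them, and whether films and MRI can be read together in the same people. The Executive Summary lists proof of concept that finger traps provide traction among the conditions for the R01, so the evidence behind it needs one definition. The reading planned in Section 9 should also answer the question as the aim puts it.

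**Working it through.** The plan gives no sample-size or power figure for Aim 2, so there is none to reproduce. The check is a side-by-side reading followed by counting.

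| Section | Arms filmed | Men / women | Link to MRI group | Visit |
|---|---|---|---|---|
| Glossary | both orthoses | not given | not given | not given |
| 1.1, footnote | 10 selected | not given | shared footnote | not relied on (table layout damaged in the copy read) |
| 3.0, Aim 2 | 5 per arm | sex matched | not given | week 2 |
| 4.3.a | 10 selected | not given | listed together | week 2 |
| 8.4.ii | arm not stated; traction orthosis | 5 / 5 | tries to include 5 | one month |
| 8.5 | all 10 on traction | 5 / 5 | not given | week 2 |
| 10.7.b | 5 per arm | 4 / 6 | the same 10 | week 2 |

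**Sex mix.** Two men and three women in each of two arms gives 2 × 2 = 4 men and 2 × 3 = 6 women, not 5 and 5. Five men cannot be divided equally between two arms, so a 5/5 group cannot be sex matched at five per arm.

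**People with specialized imaging.** Under Section 10.7.b it is 10. Under Section 8.5 at most the 5 traction-arm MRI participants can also be in the film group, so the minimum is 10 + 10 − 5 = 15. With full overlap, the film group adds 5 − 2 = 3 men and 5 − 3 = 2 women to the MRI group, giving 4 + 3 = 7 men and 6 + 2 = 8 women.

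**Share of available participants.** Assume 40 randomized at the 2:1 women-to-men target (Section 5.1), taken as 27 women and 13 men, with sex-stratified blocks of 4 (Section 6.2).
- Men: 13 = 3 full blocks (6 per arm) + 1, so 6 or 7 per arm.
- Women: 27 = 6 full blocks (12 per arm) + 3, so 13 or 14 per arm.
- Section 8.5 needs 5/7 to 5/6 = 71–83% of the traction-arm men and 5/14 to 5/13 = 36–38% of the women.
- Section 10.7.b needs 2/7 to 2/6 = 29–33% of the men and 3/14 to 3/13 = 21–23% of the women in each arm.
- If half of those randomized were men (10 per arm), the figures for men would be 5 of 10 and 2 of 10.

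**Visit windows (Section 1.1).** "Study Visit 2, Day 14 +/- 7 days" runs from Day 7 to Day 21. "Study Visit 3, Day 28 +/- 7 days" runs from Day 21 to Day 35. They share only Day 21.

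**What 5 or 10 traction hands can show.** If all n hands widen, the exact two-sided 95% lower bound on the proportion that widen is 0.025^(1/n): 47.8% for n = 5 and 69.2% for n = 10. The 95% half-width for a mean paired change, t(0.975, n−1)/√n in SDs of that change, is 1.24 for n = 5 and 0.72 for n = 10. Ten traction hands are therefore more precise, but leave no resting-orthosis hands.

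**The case against.** The strongest reply is that this is leftover drafting in two adjacent paragraphs. Only Section 8.5 says outright that all ten receive traction, and only Section 8.4.ii says one month. Correcting those two sections would restore consistency. Aim 2 is descriptive by design, and no primary endpoint, error rate or power statement rests on it. The narrowing score grades the same space, and a paired reading does address whether it opens. No figure in the documents shows that the score is too coarse, and Section 2.7 reports a visible increase on fluoroscopy in one volunteer. Preferring five per arm is also a judgement, because the aim's question is within person.

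Much of this stands. Week 2 is plainly the majority visit, the loss of sensitivity is a possibility and not a demonstrated fact, and either group is defensible. What does not follow is that the intended group is settled. Section 8.4.ii does not name an arm, but its reference to the traction orthosis and to five MRI participants fits the traction-only group of Section 8.5. That leaves two sections (3.0 and 10.7.b) against two (8.4.ii and 8.5) on who is filmed. The wording mismatch between width and narrowing score is likewise real, whatever its practical effect.

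**Conclusion.** The point holds. The group, sex mix and visit for the Aim 2 films are stated in ways that cannot all be followed, and Section 9 does not read the quantity that the aim names. The choice is between 5 traction plus 5 resting-orthosis hands with 10 people specially imaged, and 10 traction hands with no comparison and at least 15 people imaged. The counts of people follow directly from the text. The percentages of men and women depend on 40 being randomized at the 2:1 target. The consequence is moderate: it touches one whole specific aim and a stated R01 condition, but not the primary symptom or structure endpoints.

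**What to change.** 1. Adopt one group, sex mix, MRI overlap and visit, and use it in the glossary, Sections 1.1, 3.0, 4.3.a, 8.4.ii, 8.5 and 10.7.b.
   - The version in Aim 2 and Section 10.7.b (five per arm, two men and three women each, the same ten as MRI, week 2) fits the stated aim, keeps a resting-orthosis comparison and draws on fewer men. It gives up five traction hands. Only Sections 8.4.ii and 8.5 then need correcting for group and visit.
   - If ten traction hands are preferred, say so. Correct the glossary and Sections 3.0, 4.3.a and 10.7.b, split the shared footnote in Section 1.1, settle the visit and MRI overlap in Section 8.4.ii, and state that there is no control group.
2. In Section 9.0, Specific aim 2, report the with/without difference in joint space width for each person filmed, descriptively and without a test. The most symptomatic DIP is the natural joint, because Section 6.5 gives every traction participant a trap there. Other trapped joints can be listed. The narrowing score can stay as a supplement, and a mean with an interval is optional.
3. Minor wording: the MRI paragraph in Section 9.0 and the timeline in Section 10.6 call the first MRI baseline, whereas Sections 3.0, 4.3.a, 8.4.ii, 8.4.iii and 10.7.b place it at week 2. Use week 2 throughout.

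The cost is mainly text edits. Either version takes 10 people × 2 = about 20 films. Width adds one measurement per film; that this is quick is an assumption, since the documents do not say what measuring tool the reader has.

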#### **Conflict of Interests for Safety Officer:**

The Safety Officer should have no direct involvement with the study investigators or intervention. He will sign a Conflict of Interest Statement which includes current affiliations, if any, with any steering committees or advisory councils associated with the study, pharmaceutical and biotechnology companies (e.g. stockholder, consultant), and any other relationship that could be perceived as a conflict of interest related to the study and/or associated with commercial or non-commercial interests pertinent to study objectives.

### **8.7 Safety Reporting**

#### **8.7.a Adverse Event Definitions**

**Adverse Event (AE)** – Any unfavorable and unintended diagnosis, sign (including laboratory finding), symptom or disease temporarily associated with the study intervention.

- AEs may or may not be related to the intervention.
- AEs include:
  - any new events not present during the pre-intervention period or
  - events that WERE present during the pre-intervention period which have INCREASED in severity.

**Unexpected Adverse Event** – Any adverse event that is not pre-defined as a potential adverse event.

**Serious Adverse Event (SAE)** – Any untoward medical occurrence that results in:

- death or is life threatening
- requires or prolongs hospitalization

- causes persistent or significant disability/incapacity
- represents other significant hazards or potentially serious harm to research participants or others

This also includes any unanticipated problem that is definitely related to the intervention.

**Unanticipated Adverse Device Effects (UADE)** - Any serious adverse effect on health or safety or any life-threatening problem or death caused by, or associated with, a device, if that effect, problem, or death the frequency, specificity, or severity of which has not previously been identified in the investigational plan or application, or any other unanticipated serious problem associated with a device that relates to the rights, safety, or welfare of participants (21 CFR 812.)

#### 8.7.b Adverse Event Reporting

Our Research Coordinator will assess for adverse events systematically at each in clinic visit. If an adverse event is detected, he will contact [name] to complete adverse event(s) form(s) at each of those visits where the details of such adverse events will be recorded in RedCap. Additionally, should any adverse events be reported to our Research Coordinator between in clinic visits, all those events will also be recorded in RedCap by [name].

#### 8.7.c Severity Assessment of Adverse Event.

*All AEs will be assessed by the study clinician using a protocol defined grading system. The following guidelines will be used to describe severity.*

- **Mild (Grade 1)** – Events require minimal or no treatment and do not interfere with the participant's daily activities.
- **Moderate (Grade 2)** – Events result in a low level of inconvenience or concern with the therapeutic measures. Moderate events may cause some interference with functioning.
- **Severe (Grade 3)** – Events interrupt a participant's usual daily activity and may require systemic drug therapy or other treatment. Severe events are usually potentially life-threatening or incapacitating. Of note, the term "severe" does not necessarily equate to "serious".
- **Life-threatening consequences (Grade 4)**; Urgent intervention indicated.
- **Death related to AE (Grade 5)**.

#### 8.7.d Relatedness Assessment of Adverse Event.

- **Definitely Related** – There is clear evidence to suggest a causal relationship, and other possible contributing factors can be ruled out. The clinical event, including an abnormal laboratory test result, occurs in a plausible time relationship to study intervention administration and cannot be explained by concurrent disease or other drugs or chemicals. The response to withdrawal of the study intervention (de-challenge) should be clinically plausible. The event must be pharmacologically or phenomenologically definitive, with use of a satisfactory re-challenge procedure if necessary.
- **Probably Related** – There is evidence to suggest a causal relationship, and the influence of other factors is unlikely. The clinical event, including an abnormal laboratory test result, occurs within a reasonable time after administration of the study intervention, is unlikely to be attributed to concurrent disease or other drugs or

chemicals, and follows a clinically reasonable response on withdrawal (de-challenge). Re-challenge information is not required to fulfill this definition.

- **Potentially Related** – There is some evidence to suggest a causal relationship (e.g., the event occurred within a reasonable time after administration of the trial medication). However, other factors may have contributed to the event (e.g., the participant's clinical condition, other concomitant events). Although an AE may rate only as "possibly related" soon after discovery, it can be flagged as requiring more information and later be upgraded to "probably related" or "definitely related", as appropriate.
- **Unlikely to be related** – A clinical event, including an abnormal laboratory test result, whose temporal relationship to study intervention administration makes a causal relationship improbable (e.g., the event did not occur within a reasonable time after administration of the study intervention) and in which other drugs or chemicals or underlying disease provides plausible explanations (e.g., the participant's clinical condition, other concomitant treatments).
- **Not Related** – The AE is completely independent of study intervention administration, and/or evidence exists that the event is definitely related to another etiology. There must be an alternative, definitive etiology documented by the clinician.

